#### 8.4 SUBJECT POPULATION FOR SAFETY AND EFFECTIVENESS ANALYSIS

Safety analyses will be conducted an Intent to Treat (ITT) basis (i.e. all subjects who were enrolled). Primary and Secondary effectiveness analyses will be performed on a modified intent-to-treat basis (MITT; i.e. all subjects who initiated therapy, defined as subjects who initiated their first Treatment Period Visit) as will all per subject effectiveness analyses (e.g. responder analyses). Primary and Secondary endpoints (e.g. weight loss, appetite) will also be conducted on a completer, or per protocol basis (defined as those subjects that completed all visits in the study).

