#### Visit Schedule

Screening/Baseline Visit 0 (-1 week; ± 7 days) – Obtain Informed Consent prior to any study procedures. Confirm subject has met all inclusion criteria and no exclusion criteria. History & Physical including height & weight, diet history, baseline clinical parameters, provide laboratory requisition, urine pregnancy test for women of childbearing potential (WOCBP), and questionnaires. Initiate subject weekly paper diary with training for weekly completion. Subjects will be instructed to return with their weekly paper diary(ies) at their next scheduled visit.

**Enrollment/Randomization Visit 1 (Day 0; ± 7 days)** – Confirm subject continues to meet all inclusion criteria and no exclusion criteria. Assessment of T6/T7 dermatomes, clinical parameters, BP, weight, perform urine pregnancy test for WOCBP if not done at screening, administer TFEQ-R18V2 Questionnaire, assess for adverse events and changes to concomitant medications. Subjects will be randomized based on the blocked randomization algorithm.

Treatment and Control subjects will be instructed to follow a healthy 1200 calorie diet throughout the study, an electronic scale with instructions on use will be provided, and a paper diary with training for weekly completion will be provided. Subjects will be instructed to return with their paper diary(ies) at the next scheduled visit.

Only the treatment subjects will receive a handheld smartphone with the custom application and an Elira wearable patch system. It is recommended for treatment subjects to utilize an TENS Clean-Cote Skin Wipes and/or alcohol prep pad to maintain a clean application area for the treatment. Treatment subjects will also receive Cetaphil Moisturizing Lotion to be used if any irritation occurs at the treatment site. Subject will

be instructed to notify site immediately if any irritation occurs. Treatment subjects will stimulate under the supervision of the investigator or coordinator for 30 minutes prior to being discharged with the device. Treatment subjects will be assessed for toleration of the stimulation to further evaluate dose adjustment. Treatment subjects will be discharged with the Elira wearable patch system & Smartphone App and instructions on use. Treatment subjects will be instructed to return with the Elira wearable patch system and smartphone app at their next scheduled visit.

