Therapy Phase Visits 2, 3 & 4 (week 1, 4, 8 respectively; + 7 days) – Treatment and Control subjects will be assessed for adverse events and changes to concomitant medications. Obtain BP and weight. Administer the TFEQ-R18V2 Questionnaire. Collect and review paper diaries, dispense new paper diaries and review instructions for weekly completion. All subjects will be encouraged to follow a healthy 1200 calorie diet throughout the study. Subjects will be instructed to return with their paper diaries at their next scheduled visit.

Treatment subjects will be assessed for any adverse device effects (ADE), T6/T7 dermatome assessment, review and download of diary data, and stimulation adjustment (if needed). Treatment subjects will be discharged with the smartphone application and the Elira wearable patch system and instructions on use. Treatment subjects will be instructed to return with the Elira wearable patch system and smartphone app at their next scheduled visit.

End of Study Visit 5 (week 12; ± 7 days) – Treatment and Control subjects will be assessed for adverse events and changes to concomitant medications. Physical including weight, BP, requisition for laboratory tests, urine pregnancy test for WOCBP, and completion of questionnaires (PHQ9, TFEQ-R18V2, and Patient Preference Survey). Collect and review paper diaries.

Treatment subjects will return the Elira wearable patch system and the smartphone application. Treatment subjects will be assessed for ADEs and have their T6/T7 dermatome area examined.

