#### 6.1.2 Primary Effectiveness Endpoint:

The primary effectiveness endpoint is the percent reduction in total body weight loss (%TBWL), measured as End Weight – Initial Weight divided by Initial Weight, multiplied by 100, at the end of Therapy period compared to Baseline between Treatment and Control.

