## 9. STUDY PROCEDURES

The study is divided into four phases as defined below (See Appendix 6 for Schedule of Visits):

Study Phase	Definition
Screening/Baseline Visit	Obtain Informed Consent. Completion of Patient Preference Survey. Determination of Inclusion and Exclusion criteria (including PHQ-9 questionnaire; Appendix 3), Medical History and Physical, Assessment of T6/T7 Dermatomes, Obtain Concomitant Medications, Weight Loss History, Blood Pressure, Height and Weight, Blood Tests (including a lipid panel, HbA1c and CMP), and Urine Pregnancy Test for WOCBP. Dispense and Instruct on completion of Weekly Diary.
Randomization / Enrollment Visit	Confirm Inclusion/Exclusion criteria has been met, Weight, blood pressure, and AEs/Concomitant Medications assessed. Completion of baseline TFEQ-R18V2 (Appendix 4). Assessment of T6/T7 Dermatomes, UPT for WOCBP (if not done at screening),
	Randomization of subject. For both groups (control and treatment) train and dispense weekly paper diaries and electronic scale, encourage 1200 calorie diet for duration of study.
	In Addition, For Treatment Group only, training and assessment of use of smart phone app and Elira wearable patch system (Appendix 2); Initiation of therapy and dose adjustment. Provide TENS Clean-Cote Skin Wipes and/or Alcohol Prep Pads and Cetaphil Moisturizing Lotion with instructions on use as needed, dispense smart phone app and Elira wearable patch system.
Therapy Period	For Control and Treatment Groups: collect and review weekly paper diary (dispense additional diaries), weight, blood pressure, assess for AE's/concomitant medications, completion of TFEQ-R18V2, encourage continuation of 1200 calorie diet at each scheduled visit.
	In Addition, For Treatment Group only: assess for Adverse Device Effects at each visit. Collect Elira wearable patch system and smart phone and download data, assess subjects use of electronic diary completion and stimulation sessions at each visit. Dispense smart phone app and Elira wearable patch system at each visit.
End of Study Visit	For Control and Treatment Groups: Collect and review the weekly paper diary, Physical, weight, determine BMI, blood pressure, assess for AE's/concomitant medications, UPT for WOCBP, completion of PHQ9, TFEQ-R18V2, Patient Preference Survey, Blood Tests (including a lipid panel, HbA1c and CMP).

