#### 13.3 PROTOCOL DEVIATIONS

A Protocol Deviation is defined as an event where the Investigator or site personnel did not conduct the study according to the Protocol.

Investigators must approve any major deviations from the Protocol, except where necessary to protect the life or physical well-being of a subject in an emergency. Such approval shall be documented in writing and maintained in clinical study management files. Prior approval is generally not expected in situations where unforeseen circumstances are beyond the Investigator's control; however, the event is still considered a deviation and must be reported on the appropriate Case Report Form (CRF).

Deviations must be reported to the PI regardless of whether medically justifiable, pre-approved or performed to protect the subject in an emergency. Subject-specific deviations will be reported on a Protocol Deviation CRF.

Regulations require that the PI and site maintain accurate, complete and current records, including documents showing the dates of and reasons for each Protocol Deviation. For reporting purposes, Protocol Deviations are defined as major and minor as follows:

Major Deviation: Any deviation from subject Inclusion and Exclusion

criteria, subject Informed Consent procedures or

authorized device use.

Minor Deviation: Deviation from a protocol requirement such as

incomplete/inadequate subject testing procedures, follow-ups performed outside specified time windows,

etc.

Minor Deviations that continue to occur may be classified as Major Deviations if corrective action is not taken to secure future compliance to the Protocol.

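### Section 8.4 merges completer and per protocol into one supportive set defined by attendance alone, so it keeps major deviations and drops subjects with a Week 12 weight who missed an intermediate visit

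*Combined protocol and SAP*

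**What the plan says.** Section 8.4 names three analysis sets. Safety uses all enrolled subjects. Primary and secondary effectiveness use a modified intent-to-treat set: "all subjects who initiated therapy, defined as subjects who initiated their first Treatment Period Visit". The same endpoints are then repeated on a "completer, or per protocol basis (defined as those subjects that completed all visits in the study" basis. Completer and per protocol are therefore two names for one set, and no other section adds a condition to it.

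Four other places bear on this:

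- Section 13.3 sorts deviations into major and minor. The major class begins with "Any deviation from subject Inclusion and Exclusion" criteria and also covers consent procedures and authorised device use. The minor class includes incomplete testing and "follow-ups performed outside specified time windows". Section 13.3 requires reporting but links neither class to an analysis set.
- Section 6.1.2 defines the primary endpoint from two weights: "measured as End Weight – Initial Weight divided by Initial Weight, multiplied by 100".
- The Visit Schedule puts three visits between randomisation and Week 12: "Therapy Phase Visits 2, 3 & 4 (week 1, 4, 8 respectively; + 7 days".
- Section 9 has staff download device data in the treatment arm and "assess subjects use of electronic diary completion and stimulation sessions at each visit". No minimum level of use is stated.

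**The concern.** A per protocol analysis is normally read as the effect in eligible subjects treated broadly as intended. A completer analysis is read as the effect in those whose endpoint was observed. The set in 8.4 answers neither question. A subject enrolled in breach of an eligibility criterion who attends every visit is in. An eligible, compliant subject who misses only Week 1 is out, with the primary endpoint fully observed.

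What is at stake is how a supportive result is interpreted. In a study that calls itself pivotal, a result labelled per protocol will be taken as support for the primary finding. The trial is also open label, and only one arm receives a device, so attendance may differ between arms. Selection on attendance need not be neutral.

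**Working it through.** The plan gives no figure for attendance, deviations or device use, so there is no stated result to reproduce. The main check is a reading of the text. The arithmetic only shows scale.

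**1. The rule applied to three kinds of subject**

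| Subject | All visits attended | Major deviation under 13.3 | Week 12 weight | Set in 8.4 |
|---|---|---|---|---|
| Breaches an eligibility criterion, attends everything | Yes | Yes | Yes | Kept |
| Treated, attends everything, hardly stimulates at home | Yes | Unclear | Yes | Kept |
| Eligible and compliant, misses Week 1 only | No | Not named; nearest listed examples are minor | Yes | Dropped |

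The second row is unclear because 13.3 defines a deviation as a failure by the investigator or site staff to follow the protocol. A subject's own non-use may not qualify.

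**2. Share dropped although the endpoint was observed**

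Inputs: 75 per group and 30% dropout (section 8.2); three intermediate visits (Visit Schedule, Appendix 6). Assumed, not in the documents: a miss probability m per visit among those who reach Week 12, independent across visits.

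Reaching Week 12: 75 × 0.70 = 52.5 per group. Share dropped: 1 − (1 − m)³.

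| m | Share dropped | Dropped per group | Left per group | Left as share of 75 |
|---|---|---|---|---|
| 2% | 1 − 0.98³ = 5.9% | 3.1 | 49.4 | 66% |
| 5% | 1 − 0.95³ = 14.3% | 7.5 | 45.0 | 60% |
| 10% | 1 − 0.90³ = 27.1% | 14.2 | 38.3 | 51% |
| 15% | 1 − 0.85³ = 38.6% | 20.3 | 32.2 | 43% |

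Independence matters. If the same subjects miss all three visits, the share dropped is only m. If no subject misses more than one, it is 3m. At m = 5% the possible range is therefore 5% to 15%.

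**3. Effect of retained non-users**

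Section 8.2 assumes 7.5% against 3.5% weight loss, a difference of 4.0 points. If a fraction f of retained treated subjects barely use the device and lose weight like controls, the expected difference is 4.0 × (1 − f). For f = 5%, 10%, 20% and 30% this is 3.8, 3.6, 3.2 and 2.8 points. The values of f are assumptions.

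**4. Is this a power problem?**

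Take power as Φ(Δ / (SD × √(2/n)) − 1.96), with SD 5 from section 8.2. Two-sided 0.05 is assumed from the 95% intervals in section 8, because no alpha is stated for the primary test.

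- Missed visits, Δ = 4.0: n = 49.4, 45.0, 38.3 and 32.2 give 97.8%, 96.7%, 93.8% and 89.5%.
- Non-use, n = 52.5: Δ = 3.8, 3.6, 3.2 and 2.8 give 97.3%, 95.8%, 90.6% and 81.8%.

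Taken one at a time, neither mechanism brings power below about 82% at the design values. The problem is who is in the set and what the result means, not mainly power.

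**The case against.** The strongest reply is that this is only a supportive set. The primary and secondary effectiveness analyses are modified intent-to-treat, no success rule depends on the attendance-based set, and no observed weight is lost from the primary analysis. That stands, and it limits the point to a supportive result.

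Four stronger readings are tempting, and the documents do not support them:

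- *A treated subject who never stimulated would count as per protocol.* The Visit Schedule says "Treatment subjects will stimulate under the supervision of the investigator or coordinator for 30 minutes prior to being discharged with the device", and section 5 also requires an in-office session. Never stimulating would itself breach Visit 1 procedures. What the documents support is little or no home stimulation afterwards. Section 16.5 ends participation for non-compliance, but it sets no threshold, does not mention analysis sets, and has no counterpart among the discontinuation reasons in section 7.3.
- *Stimulation data go unused.* They are unused only for set membership. Sections 8, 8.1.2, 8.1.3 and 8.2 relate stimulation to endpoints, appetite and weight loss.
- *A missed visit has nothing to do with the outcome.* Visits 2 to 4 include diet encouragement, diary review and stimulation adjustment, so attendance is part of adherence. Requiring it can be defended for a per protocol set. It is hard to defend for a completer set when the endpoint was observed.
- *Ineligible subjects will be common.* Eligibility is checked at Visits 0 and 1 and medications are reviewed at every visit. The point is only that the rule would not remove the errors that do occur.

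**Conclusion.** The point holds as a defect in a supportive analysis set. Section 8.4 gives one set two names and defines it by attendance alone. It keeps major deviations and treated subjects with little home use, and it drops subjects whose primary endpoint is complete. This follows from the text and needs no numerical assumption.

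Its size cannot be known from the documents. Under independent misses of 2%, 5% or 10% per visit, about 6%, 14% or 27% of those reaching Week 12 would be dropped; correlated misses would lower these shares. The result would be mislabelled and needlessly selected. A reader should not infer that the primary conclusion is at risk, because the modified intent-to-treat analysis does not use this set.

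**What to change.** Amend section 8.4 to define two sets, both supportive:

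- **Completers:** randomised subjects with a Week 12 clinic weight, whatever intermediate visits they missed.
- **Per protocol:** completers with no major deviation under section 13.3, with the exclusion list fixed before outcome data are analysed.

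State how off-window visits and early termination visits count. Section 13.3 allows repeated minor deviations to be reclassified as major, so any reclassification should be settled in the same review.

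A device-use criterion should be optional. If the sponsor wants one, the sponsor should set it in advance and say how approved session changes enter the denominator. It should be reported with the caveat that, applied to the treatment arm alone in an open-label trial, it compares adherent treated subjects with unselected controls and may inflate the effect. Without it, some low-use treated subjects stay in the per protocol set, which the report should say.

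The cost is SAP wording and a deviation review before analysis. The Week 12 weight and the deviation case report form are already collected. The per protocol comparison remains non-randomised and supportive.

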#### 8.5 DEVIATIONS FROM THE STATISTICAL ANALYSIS PLAN

Any deviations in the analysis of the final data set from the statistical analysis plan will be documented and justified in the final report.

## 9. STUDY PROCEDURES

The study is divided into four phases as defined below (See Appendix 6 for Schedule of Visits):

Study Phase	Definition
Screening/Baseline Visit	Obtain Informed Consent. Completion of Patient Preference Survey. Determination of Inclusion and Exclusion criteria (including PHQ-9 questionnaire; Appendix 3), Medical History and Physical, Assessment of T6/T7 Dermatomes, Obtain Concomitant Medications, Weight Loss History, Blood Pressure, Height and Weight, Blood Tests (including a lipid panel, HbA1c and CMP), and Urine Pregnancy Test for WOCBP. Dispense and Instruct on completion of Weekly Diary.
Randomization / Enrollment Visit	Confirm Inclusion/Exclusion criteria has been met, Weight, blood pressure, and AEs/Concomitant Medications assessed. Completion of baseline TFEQ-R18V2 (Appendix 4). Assessment of T6/T7 Dermatomes, UPT for WOCBP (if not done at screening),
	Randomization of subject. For both groups (control and treatment) train and dispense weekly paper diaries and electronic scale, encourage 1200 calorie diet for duration of study.
	In Addition, For Treatment Group only, training and assessment of use of smart phone app and Elira wearable patch system (Appendix 2); Initiation of therapy and dose adjustment. Provide TENS Clean-Cote Skin Wipes and/or Alcohol Prep Pads and Cetaphil Moisturizing Lotion with instructions on use as needed, dispense smart phone app and Elira wearable patch system.
Therapy Period	For Control and Treatment Groups: collect and review weekly paper diary (dispense additional diaries), weight, blood pressure, assess for AE's/concomitant medications, completion of TFEQ-R18V2, encourage continuation of 1200 calorie diet at each scheduled visit.
	In Addition, For Treatment Group only: assess for Adverse Device Effects at each visit. Collect Elira wearable patch system and smart phone and download data, assess subjects use of electronic diary completion and stimulation sessions at each visit. Dispense smart phone app and Elira wearable patch system at each visit.
End of Study Visit	For Control and Treatment Groups: Collect and review the weekly paper diary, Physical, weight, determine BMI, blood pressure, assess for AE's/concomitant medications, UPT for WOCBP, completion of PHQ9, TFEQ-R18V2, Patient Preference Survey, Blood Tests (including a lipid panel, HbA1c and CMP).
	In Addition, For Treatment Group only: assess for Adverse Device Effects, collect Elira Wearable patch system and smart phone and download data, assess subjects use of electronic diary completion and stimulation sessions. Assess T6/T7 dermatomes.

#### 9.1 INFORMED CONSENT

Prior to subject participation in this study, the PI or designee must obtain written Institutional Review Board (IRB) approval for the protocol and the Informed Consent Form.

Once the subject's eligibility has been determined, the Investigator or person designated by the Investigator who has been trained to the Protocol, will explain the nature and scope of the study, discuss potential risks and benefits of participation, answer all questions from the subject and ask the subject to participate in the study. The study will be explained to the study subject in lay terms. If the subject agrees to participate, the Informed Consent must be personally signed and dated by the subject and the Investigator or person designated by the Investigator. Any additional persons required to sign the Informed Consent by the IRB will also do so. A copy of the signed and dated Informed Consent must be provided to the study subject. Study subjects will be assured that they may withdraw from the study at any time and for any reason.

Failure to obtain a signed Informed Consent prior to the procedure constitutes a major Protocol deviation.

#### 9.2 SCREENING PROCEDURES

All candidates must be screened for eligibility. A member of the research team assigned to the study should review the subject's medical history to screen for eligibility.

The following tests and procedures must be performed prior to TENS therapy:

- Physical examination, medication history, height, weight and BMI.
- Relevant medical history including subject demographic information and weight loss history.
- Patient Preference Survey and PHQ-9.
- Urine Pregnancy Test (UPT) for WOCBP; blood lipid panel, CMP and HbA1c.

#### 9.3 PHYSICAL EXAMINATIONS

A general physical examination will be performed as well as an examination of organ systems (central nervous system [CNS], cardiac, peripheral vascular, pulmonary, musculoskeletal, abdominal, dermatologic and lymphatic). The dermatologic exam will focus on Dermatome T6-T7 site for any active disease, scars, tattoos, or other problems that would make the site unacceptable for the TENS Unit. Depilation by waxing, shaving, chemical depilatories or any other method in the selected application site is not allowed during the study.

#### 9.4 BODY MASS INDEX

Height and weight without shoes will be used to determine body mass index (BMI) in accordance with the BMI Chart (15,16; Appendix 1) and confirmed by NIH BMI Calculator. Subjects will be encouraged to wear the same or similar clothing at each visit for more consistent weight measurements.

#### 9.5 MEDICAL HISTORY AND DEMOGRAPHICS

A complete medical history evaluation, including surgical history and demographic data (age, gender, race, ethnicity, and highest level of education) and weight loss history will be obtained for each subject.

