#### 5.3 ASSIGNMENT & BLINDING

Subjects meeting the Inclusion and Exclusion criteria will be enrolled and randomized into either Treatment or Control groups. The randomization algorithm will be blocked to account for site bias and to ensure counterbalance across sites. As this is an open label study, there will be no consideration for blinding.

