### 8. STATISTICAL CONSIDERATIONS AND ANALYSIS PLAN

Categorical variables will be summarized by number and percent. Continuous variables will be summarized by total number (N), mean, standard deviation (SD), median, minimum and maximum. Ninety-five percent, 2-sided confidence intervals on estimated means and differences in means between treatment and control groups will be calculated. Confidence intervals will be similarly computed for proportions and differences between proportions. In addition, propensity score and sensitivity analyses will be utilized to compare adverse events and/or adverse device effects incidence versus historical control. Wilcoxon signed rank tests, Fisher exact tests, and Pearson Correlations will be utilized to compare changes in baseline variables between varying

time points of the study (e.g. baseline versus post stimulation treatment) and to correlate stimulation parameters with endpoint values. Markov-chain Monte Carlo Analyses will be utilized to conduct Bayesian posterior probability distributions with multiple imputations allowed to assess treatment efficacy within and between cohorts. The need for additional endpoints to achieve primary and secondary significance will be determined utilizing longitudinal modeling. Finally, dose response will be modeled and analyzed within and between cohorts to determine optimal therapy dose for stimulation in open label period within and between cohorts using Normal dynamic linear modeling (NDLM) since monotonicity of the response cannot be assumed.

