#### 8.1.3 Weight Loss

The null and alternative hypotheses are:

$$H_0$$
:  $π_T ≤ π_C$ 
 $H_1$ :  $π_T > π_C$ 

Where  $\pi_T$  and  $\pi_C$  are the probabilities of weight loss (% TBWL, %EBWL) in treatment versus control respectively. Estimates of the proportion of weight loss in pounds, % total body weight loss (%TBWL) Excess Body Weight Loss (%EBWL) or BMI will be compared with a tested Fishers Exact Test. Estimates and 95% confidence intervals will also be computed for the difference in rate of weight loss between varying stimulation levels.

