#### 9.10 **DIET**

Subjects will be encouraged to maintain a healthy 1200 calorie diet throughout the study. The study doctor and/or research coordinator will provide guidance to assist the subjects on maintaining the diet.

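### Sections 8 and 8.1.3 compare weight loss without the recorded baseline covariates; a prespecified adjustment is a nearly free gain in precision, with no bias at issue

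*Combined protocol and SAP*

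**What the plan says.** Section 6.1.2 defines the primary effectiveness endpoint as %TBWL, "measured as End Weight – Initial Weight divided by Initial Weight, multiplied by 100", compared between Treatment and Control. For estimation, section 8 says "Ninety-five percent, 2-sided confidence intervals on estimated means and differences in means between treatment and control groups will be calculated". Section 8.1.3 writes its hypotheses on two parameters that "are the probabilities of weight loss (% TBWL, %EBWL) in treatment versus control respectively", and says the weight-loss measures "will be compared with a tested Fishers Exact Test".

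Neither section names a covariate for weight loss. The one adjustment method in section 8, a propensity score, is reserved for adverse events against a historical control. The MCMC, longitudinal and NDLM analyses are listed without baseline covariates.

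The data needed for adjustment are collected. Section 9.5 states that "demographic data (age, gender, race, ethnicity, and highest level of education) and weight loss history will be obtained for each subject", and Appendix 6 schedules weight at Visit 0 and Visit 1. On allocation, section 5.3 says "The randomization algorithm will be blocked to account for site bias and to ensure counterbalance across sites"; no sex, size or age stratum is mentioned. On diet, section 9.10 says "Subjects will be encouraged to maintain a healthy 1200 calorie diet throughout the study", with no variation by sex or size.

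**The concern.** A baseline variable that predicts the outcome, but is left out of the model, stays in the error term. The interval is then wider than it need be, and a chance difference between arms in that variable moves the estimate.

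The plan's own design gives a reason to expect sex and body size to matter. BMI 25-35 over the Appendix 1 heights (152.4 to 193.0 cm) spans about 25 × 1.524² = 58 kg to 35 × 1.930² = 130 kg. A single target of 1200 calories supplies 1200/58 = 20.7 per kg at one end and 1200/130 = 9.2 per kg at the other. Dividing weight change by initial weight does not by itself remove that difference. How far it carries through to %TBWL depends on energy need and adherence, and the documents give neither. This argument does not extend to age.

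**Working it through.** **Inputs.** From section 8.2: means 3.5% and 7.5% (difference 4.0 points), SD 5, 80% power, 30% dropout, 75 per group. The two-sided 0.05 level is an assumption taken from the 95% two-sided interval in section 8. The share of variance explained by the covariates (R²) is not in the documents; 5%, 10% and 20% are assumed, with zero as a check.

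**The plan's own figure.** The standard formula for two means gives n = 2 × (1.960 + 0.842)² × 5² / 4² = 24.5, so 25 evaluable per arm, and 25/0.70 = 36 enrolled. This does not reproduce 75. The adaptive model behind 75 is not specified, so 75 cannot be called wrong on this basis. It is used below as the planned size.

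**Which n.** Section 8.4 analyses everyone who initiated therapy and section 8.3 carries the last value forward, so the primary set is close to 75 per arm. The completer set is about 75 × 0.70 = 52.5, taken as 52.

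**Unadjusted half-width** = 1.96 × 5 × √(2/n):
- n = 75: 1.96 × 0.816 = 1.60 points
- n = 52: 1.96 × 0.981 = 1.92 points

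**Adjusted half-width.** With three covariates (weight, sex, age) and N subjects in total, multiply by √[(1 − R²) × (1 + 3/(N − 6))]. The second term is the price of estimating three extra coefficients.

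| R² (assumed) | Factor, N = 150 | Half-width | Factor, N = 104 | Half-width |
|---|---|---|---|---|
| 0.05 | 0.985 | 1.58 | 0.989 | 1.90 |
| 0.10 | 0.959 | 1.53 | 0.963 | 1.85 |
| 0.20 | 0.904 | 1.45 | 0.908 | 1.75 |

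Simulation with 2000 runs per setting gave ratios of 0.985, 0.958 and 0.903 at 75 per arm, and 0.991, 0.963 and 0.907 at 52.

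**In subjects.** n divided by the squared factor gives 77.3, 81.6 and 91.8 per arm from 75, or about 5, 13 and 34 subjects in total. From 52 it gives 53.1, 56.1 and 63.1, or about 2, 8 and 22.

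**Price if the covariates are useless.** At R² = 0 the factor is √(1 + 3/144) = 1.010, or √(1 + 3/98) = 1.015. Break-even R² is 1 − 1/1.0208 = 2.0% at N = 150 and 1 − 1/1.0306 = 3.0% at N = 104.

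**Site.** The table does not price site terms. Up to 10 centres means up to 9 terms. Blocking by site keeps these nearly balanced, so their true price is small. As a ceiling that ignores the blocking, 11 terms (weight, sex and 9 for site) give √(1 + 11/136) = 1.040 at N = 150 before any variance is explained.

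**Chance imbalance.** The part of the unadjusted estimate's sampling error due to the covariates has 95% limits of ±1.96 × √R² × SE. That is ±0.36, ±0.51 and ±0.72 points at 75 per arm, and ±0.43, ±0.61 and ±0.86 at 52.

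**Sex alone.** With 20-50% men and a 1-3 point sex gap in %TBWL (both assumed), R² = p(1 − p) × gap²/25 = 0.006 to 0.09. This range runs from below break-even to well above it.

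**Power.** Φ(4.0/0.816 − 1.96) = 99.8% at 75 per arm; Φ(4.0/0.981 − 1.96) = 98.3% at 52.

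**The case against.** The best case for leaving the plan alone is that nothing in it is invalid and no planned decision changes. Several stronger readings are tempting, and the documents do not support them.

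- *The unadjusted result is biased, or its error rate is wrong.* It is neither. The arms are randomised, so the unadjusted difference is unbiased and keeps its type I error.
- *Chance imbalance is an extra, unaccounted error.* It is already inside the ±1.60 or ±1.92. Adjustment removes that part; it does not repair an omission from the interval.
- *The trial lacks power without adjustment.* On the plan's own inputs it does not. Precision matters more if the true difference is well below 4 points: 80% power at 75 per arm corresponds to 2.8 × 0.816 = 2.29 points. The Protocol Summary does allow enrolment of up to 300.
- *The fixed diet makes sex and size predictive by design.* It makes this plausible. The diet is only encouraged, %TBWL already divides by initial weight, and the documents give no R², sex mix or energy need.
- *Adjustment costs nothing.* It costs little: at R² below 2-3% the interval widens slightly.

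It is also fair to say that covariate choice comes second to a larger gap: the endpoint is continuous, yet 8.1.3 tests proportions, and no passage names a primary model. That objection affects how the fix is worded and does not remove the point. The MCMC and longitudinal analyses do not answer it either, since they name no baseline covariates.

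**Conclusion.** The point holds as a low-cost improvement in precision. The plan omits baseline covariates that it already collects, and the site factor on which it blocks, from its weight-loss comparison. At about 75 per arm the interval would narrow by roughly 1.5%, 4% or 10% at an assumed R² of 5%, 10% or 20%, and completers would gain almost the same. Those figures rest on the planning SD of 5, on three covariates, and on an R² that the documents do not supply. The downside if the covariates predict nothing is 1-1.5%. Validity and nominal power are not in question. Naming the covariates in advance also matters in an open-label trial, because it settles beforehand whether adjustment was chosen after seeing results. The case is stronger for sex and body size than for age.

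**What to change.** In 8.1.3, state that the primary between-arm estimate is the adjusted mean difference in %TBWL, with its 95% interval, from a linear model with arm, pre-randomisation weight, sex and site as prespecified covariates; age is optional. Say which pre-randomisation weight is used (Visit 0 or Visit 1), and use the same one as the initial weight in the endpoint. Report the unadjusted difference in means as supportive.

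For the >5% responder endpoint, keep the difference in proportions planned in section 8. If a covariate-adjusted version is added, report it as a standardised risk difference and not as an odds ratio alone, which would change the quantity being estimated.

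The cost is SAP wording. No new data, visits or subjects are needed, and the continuous primary endpoint gains the named model that it now lacks.
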